Protocol summary

Study title	Intra-operative vessel and bone acquisition, towards ultrasound registration for surgical navigation NL: Intra-operatieve beeldvorming van de vaten en botten, voor toekomstige navigatie chirurgie met ultrasound registratie
Study coordinator	[name], MSc
Co-investigator(s)	[name]. [name], surgical oncologist Dr. [name] Dr. [name] Dr. [name] Dr. [name]
Rationale	Image-guided navigation surgery allows for full utilization of pre-operative imaging during surgery and has the potential of reducing both irradical resections and morbidity. To use navigation, a registration procedure is required to correlate pre-operative imaging with the patient's position on the operating room (OR). Currently, registration is done by Cone-Beam CT (CBCT) scanning on the OR prior to navigation surgery. However, the main limitation of the CBCT method is that it cannot compensate for per-operative changes such as bed rotation, retractor placement and tissue displacement due to the surgery. Alternatively, by using intra-operative tracked ultrasound and vessel-based patient registration, changing conditions during surgery can better be dealt with. This improved patient registration method could lead to an increased navigation accuracy and improved clinical usability and outcomes. The main difference between CBCT and proposed ultrasound registration is that CBCT is based on bones, while the ultrasound is based on vessels. Bones can be very easily imaged on the CBCT and therefore used for bone-bone registration with pre-operative CT-scans. However, vessels are more difficult to acquire, especially with ultrasound, and an automatic registration process with pre-operative imaging is needed for efficient clinical usability. For this, the vessels need to be extracted from the tracked ultrasound images to create a 3D representation that can be registered. Therefore, an algorithm needs to be developed that can automatically segment the vessels from ultrasound images.
Objectives	Primary objective: 
To develop an automatic segmentation algorithm using artificial intelligence for real-time intra-operative vessel segmentation Secondary objectives: 
Post-operative evaluating the accuracy of different registration

	
methods, such as 3D model or centerline registration
 
 • The usability of the tracked ultrasound setup (SUS-score)
Study design	A single center observational feasibility study
Methodology	
This is a feasibility study, without any impacts on the surgical procedure itself. The total study-related delay of the surgical procedure will be approximately 10 minutes. Participation in the study will not involve additional visits to the hospital or additional radiation dose for the included patients. Informed consent will be obtained during the pre-operative outpatient clinic appointment or upon admission to the hospital at least one day before operation.
 
Surgery starts according to the standard procedure, which includes incision and preparation of the internal tissue required for the surgery. For this study, optimal ultrasound image acquisition of the vessels (without compressing the tissue with the ultrasound probe) is required. For laparotomy, the abdominal cavity will partly be filled with standard warm saline. Subsequently, intra-abdominal ultrasound is acquired using the BK ultrasound system linked to the NDI Aurora electromagnetic tracking system. For robotic assisted lymph node dissections, intra-operative ultrasound could be acquired percutaneously and/or intra-abdominal using a drop-in ultrasound transducer. If accessible, the abdominal aorta, left and right iliac arteries and both internal and external iliac arteries will be imaged as well as the pubic bone, sacrum and iliac crests; or other relevant arteries and bones close to the target area. For offline validation of the registration accuracy, a sterile electromagnetic pointer is used to pinpoint several anatomical landmarks, such as the aortic bifurcation or lymph nodes. All ultrasound and tracking data will be recorded during the measurements and post-operatively analyzed and used to train an automatic vessel segmentation algorithm.

Inclusion criteria	
 • Age ≥ 18 • Patients scheduled for laparotomy (first 30 patients) or robotic assisted lymph node dissection (second 20 patients) • A pre-operative CT scan is available • Patients provide written ‘informed consent’
Exclusion criteria	
 • Metal implants which could influence the vessel segmentation or tracking accuracy • Pacemaker or defibrillator • Patient received treatment, e.g. surgery or radiotherapy, between the pre-operative CT scan and surgery, which might altered the patient’s anatomy
Number of patients	50 (firstly 30 laparotomy patients, secondly 20 robotic assisted lymph node dissection patients)
Study duration	2 years

Evaluation criteria	
 Number and quality of ultrasound sweeps for automatic segmentation of the vessels Localization of clinical targets with an electromagnetically tracked pointer to compute a target registration error
Statistical methods	
The main study parameter is the development of an algorithm that can automatically segment the vessels from US imaging. With this study, we want to obtain intra-operative US data to train such algorithm. Statistically, we want to test if the created algorithm is able to successfully segment the vessels from US images. This can be done by comparing the automatically segmented vessel with the ground truth. The segmentation will be defined successful for a Dice coefficient ≥ 0.7.
 
Since we are interested in the proportion of vessels found on US images, the sample size was calculated with a power calculation based on the number of US sweeps. It is assumed that the US image quality and the number of found vessels are equally correlated across different patients, since we use a scanning protocol to visualize the same vessel segments in each patient. The segmentation of an US sweep will be defined successful for a Dice coefficient ≥ 0.7 of that sweep. We estimate a success rate of the network to successfully segment the main pelvic arteries in all sweeps combined of 93% (P). According to the binomial calculation using a 95% confidence interval for proportion with a width of 0.1, a sample size of 118 US sweeps is required. In this study, at least 4 US sweeps will be made per patient, which means that 30 patients should be included for a total of 120 US sweeps.
 
After successful evaluation of these 30 laparotomy patients, the same methods will be applied to 20 patients scheduled for robotic assisted lymph node dissection.
 
In addition, the registration accuracy will be determined by computing the target registration error. The usability of the tracked ultrasound setup will be evaluated using standard questionnaires, resulting in a score between 1 and 100.

Quality of Life	N.A.
Pharmakinetics (PK)	N.A.
Translational research (TR)	N.A.
Risk evaluation	No additional burden or risks are expected apart from the extended surgery time, approximately 10 minutes, for the included patients. Ultrasound imaging takes place in the same way that conventional intra-operative ultrasound is acquired (for example during liver surgeries), using the same standardized sterile cover or sterilized US transducer. The electromagnetic tracking system (NDI Aurora) including the tracked pointer is the same system as applied during conventional abdominal navigated surgeries at the NKI-AvL and multiple navigation studies.

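### The sample size of 118 sweeps treats sweeps as independent, although they come in groups of at least four per patient and correlation within a patient is not addressed

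*Combined protocol and SAP*

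**What the plan says.** All of this is in the Protocol summary, Statistical methods row.

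- The unit of the calculation is the sweep: "the sample size was calculated with a power calculation based on the number of US sweeps". A sweep succeeds if its Dice coefficient is at least 0.7.
- The success proportion is pooled over all sweeps and expected to be 93%.
- The precision target gives the number of sweeps: "a 95% confidence interval for proportion with a width of 0.1, a sample size of 118 US sweeps is required".
- Sweeps are converted to patients: "In this study, at least 4 US sweeps will be made per patient, which means that 30 patients should be included", for 120 sweeps in total.
- On correlation the plan says only "It is assumed that the US image quality and the number of found vessels are equally correlated across different patients", with the reason "since we use a scanning protocol to visualize the same vessel segments in each patient".

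No ICC, design effect or clustered interval is given, and the method for the final interval is not stated.

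**The concern.** Four sweeps from one patient share that patient's anatomy, surgical access and scanning conditions, and are taken within one short session. If some patients are easier to segment than others, their sweeps tend to succeed or fail together, and 120 sweeps then carry less information than 120 independent ones.

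The sentence on equal correlation does not deal with this. Equal correlation is not zero correlation. Scanning the same segments in every patient makes patients comparable with one another; it does not make the sweeps of one patient independent.

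The interval width is the only stated basis for 30 patients, so the study's one precision claim is at stake. If the planning method is reused for the final analysis, the reported interval will keep about its planned width whatever the correlation, and the reader will not see that its coverage has dropped.

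**Working it through.** **Inputs from the plan:** P = 0.93; 95% interval of width 0.1; 118 sweeps; at least 4 sweeps per patient; 30 patients; 120 sweeps.

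**Assumed, because the plan does not give them:** the ICC (shown as a range), exactly m = 4 sweeps per patient unless stated, and all 120 sweeps used for evaluation.

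**Step 1. Reproduce 118.** Take the smallest n for which the exact (Clopper-Pearson) interval with x = round(0.93n) successes is at most 0.1 wide.

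- n = 117, x = 109: width 0.1003
- n = 118, x = 110: 0.871 to 0.970, width 0.0995

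The plan's figure is reproduced by a formula that assumes independent sweeps. Other common intervals give different answers (Wald 101, Wilson 107, Agresti-Coull 115).

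**Step 2. Slack in the rounding.** The design effect is 1 + (m − 1) × ICC. Going from 118 to 120 sweeps absorbs an ICC of (120/118 − 1)/3 ≈ 0.006.

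**Step 3. Precision with clustering.** Effective n = 120/(1 + 3 × ICC). For example, at ICC 0.2 it is 120/1.6 = 75. The width is the Clopper-Pearson width at x = 0.93 × effective n, with x not rounded. On this basis ICC 0 gives 0.0999; rounding to 112/120 gives 0.0979.

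**Step 4. Coverage if clustering is ignored.** The count per patient is taken as beta-binomial(4, 0.93, ICC). Convolving 30 such counts gives the exact distribution of the total, and hence the coverage of the unadjusted exact interval on 120 sweeps. Its mean width stays at about 0.098 throughout.

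| ICC | Design effect | Effective n | Width | Unadjusted coverage |
|---|---|---|---|---|
| 0 | 1.00 | 120 | 0.100 | 97.1% |
| 0.05 | 1.15 | 104 | 0.108 | 95.9% |
| 0.1 | 1.30 | 92 | 0.115 | 94.6% |
| 0.2 | 1.60 | 75 | 0.129 | 91.8% |
| 0.3 | 1.90 | 63 | 0.142 | 89.0% |

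Coverage falls below 95% once the ICC exceeds 0.084.

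**Step 5. Sensitivity.**

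- *Other true proportions.* For P = 0.85, 0.90 and 0.95 the crossing is at ICC 0.03, 0.07 and 0.06, and coverage at ICC 0.2 is 89.4%, 91.0% and 90.9%.
- *More sweeps per patient.* With 6 each (180 sweeps), the width at ICC 0.1, 0.2 and 0.3 is 0.100, 0.117 and 0.132. Unadjusted coverage falls to 93.0%, 88.3% and 83.7%, because the unadjusted interval narrows to about 0.079.
- *Differences between vessel segments.* Fixed differences pull slightly the other way. With assumed segment success rates of 0.99, 0.98, 0.90 and 0.85 (mean 0.93), the variance is 0.95 of binomial.

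**Step 6. Does a clustered interval work with 30 patients?** Beta-binomial simulation, P = 0.93, m = 4, 100,000 trials per cell; each cell gives coverage and mean width:

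| ICC | Exact at estimated effective n, t(29) | Logit, cluster-robust, t(29) |
|---|---|---|
| 0 | 97.8%, 0.105 | 96.6%, 0.099 |
| 0.1 | 97.3%, 0.117 | 96.1%, 0.113 |
| 0.2 | 96.5%, 0.129 | 95.2%, 0.126 |
| 0.3 | 95.6%, 0.141 | 94.2%, 0.139 |
| 0.5 | 94.0%, 0.163 | 92.5%, 0.163 |

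Both hold close to or above 95% up to ICC 0.3.

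**The case against.** The arithmetic is not in dispute. The case on the other side is about weight.

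- **The harm is conditional.** The documents give no evidence on the ICC. At 0.05 the width is 0.108 and the unadjusted interval still covers 95.9%; coverage of 92% or less needs an ICC of about 0.2. This stands, and is why the size is given as a range.
- **More than 4 sweeps per patient are allowed.** With 6 each and ICC 0.1 the width is back at 0.100. That is true only under a clustered analysis; without one, the extra sweeps make coverage worse.
- **Little turns on the interval.** This is a single-centre feasibility study with no pass mark tied to the interval, and the step to the robotic cohort has no numerical criterion. This stands and limits the severity.
- **The evaluation set may be smaller.** The recordings are to be used for training, and no separate evaluation set is described. If 10 of the 30 patients were held out (an assumption), the exact width would be about 0.18 at ICC 0 and 0.21 to 0.27 at ICC 0.1 to 0.3, so clustering might be the lesser threat to precision. This is a fair caution. But evaluating all 120 sweeps is the premise of the plan's own calculation, and a held-out set would still be clustered by patient. Any restated width must name the number of patients and sweeps evaluated.

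**Conclusion.** The concern holds and should be fixed. The 118 sweeps come from an independent-observation formula, and the sentence on correlation does not cover sweeps within a patient. With 4 sweeps per patient, P = 0.93 and all 120 sweeps evaluated, any ICC above about 0.006 takes the expected width, on the planning formula, past 0.1. Widths of 0.115 to 0.142 correspond to an assumed ICC of 0.1 to 0.3. If clustering is ignored in the analysis, coverage drops below 95% at an ICC of about 0.08 and to 89.0% at 0.3, with no visible sign in the reported width. The omission is certain; its size depends on an ICC that the documents do not give. It affects the precision and coverage of the main result, not a decision rule.

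**What to change.** Keep 30 patients and change the following:

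1. Replace the sentence on equal correlation with a statement that sweeps are clustered within patients.
2. Specify a patient-clustered 95% interval for the sweep success proportion. Two suitable choices are an exact interval at the estimated effective sample size with a t adjustment, or a logit-scale interval with a cluster-robust standard error and t quantiles. Degrees of freedom are the number of patients evaluated minus one: 29 if all 30 are used.
3. State what is done if every sweep succeeds, when the ICC cannot be estimated: use the exact interval with the patient as the unit (30 if all are evaluated). In simulation this occurred in at most 0.3% of trials up to ICC 0.3.
4. Restate the expected width as about 0.115 to 0.142 for an ICC of 0.1 to 0.3, with 4 sweeps per patient and all 120 evaluated. Recalculate it if some patients are held out.
5. Report the estimated ICC.

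The cost is some protocol wording and a few lines of analysis code, with no extra patients. The stated precision becomes less favourable. If the sweeps prove independent, little is lost: the two intervals average 0.105 and 0.099 wide at ICC 0. Holding the width at 0.1 by recruitment instead would take 118 × 1.3 to 118 × 1.9, or 154 to 225 sweeps (39 to 57 patients at 4 each), for ICC 0.1 to 0.3. That is not proposed here.

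### Does the freedom to image other arteries undermine the pooled success rate for the main pelvic arteries?

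*Combined protocol and SAP*

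**What the plan says.** All of this is in the protocol summary.

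- **Statistical methods, comparability.** "It is assumed that the US image quality and the number of found vessels are equally correlated across different patients", and the reason given is that "we use a scanning protocol to visualize the same vessel segments in each patient".
- **Statistical methods, planned rate.** "We estimate a success rate of the network to successfully segment the main pelvic arteries in all sweeps combined of 93% (P". A sweep succeeds if its Dice coefficient is 0.7 or more; no vessel is named in that rule.
- **Statistical methods, size.** A 95% interval of width 0.1 requires 118 sweeps. With a minimum of four sweeps per patient, "30 patients should be included for a total of 120 US sweeps".
- **Methodology, what is imaged.** "If accessible, the abdominal aorta, left and right iliac arteries and both internal and external iliac arteries will be imaged", together with pelvic bones, "or other relevant arteries and bones close to the target area". The sentence just before it concerns the second cohort: "For robotic assisted lymph node dissections, intra-operative ultrasound could be acquired percutaneously and/or intra-abdominal using a drop-in ultrasound transducer".
- **Inclusion criteria.** "Patients scheduled for laparotomy (first 30 patients" describes the cohort on which the calculation rests. No surgical site is specified.

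**The concern.** The case for pooling sweeps is that every patient contributes the same anatomy. The Methodology section allows the anatomy to vary: listed arteries may be out of reach, and others may be imaged instead. That sentence follows the one on robotic surgery but is not restricted to that cohort, and a laparotomy need not be pelvic.

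Two things would be at stake. First, a rate described as applying to the main pelvic arteries could include sweeps of something else. The summary does not say whether the aorta is one of those arteries, or what happens to a sweep that shows none of them. Second, the margin over 118 is thin. At four sweeps per patient, more than two sweeps without a target artery would leave fewer than planned.

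**Working it through.** **Inputs from Statistical methods:** P = 0.93, 95% confidence, full width 0.10, 118 sweeps, 30 patients, at least 4 sweeps each. **Assumed, because the documents give no value:** the share u of sweeps showing other arteries, and their success rate s.

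**1. The plan's own figure.** The exact (Clopper-Pearson) limits for x successes in n sweeps are the 0.025 quantile of Beta(x, n − x + 1) and the 0.975 quantile of Beta(x + 1, n − x), with x taken as 0.93n rounded.
- n = 117: 0.93 × 117 = 108.81, so x = 109; width 0.1003.
- n = 118: 0.93 × 118 = 109.74, so x = 110; limits 0.8708 and 0.9703; width 0.0995.

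So 118 is the smallest n that meets the target. Then 118 / 4 = 29.5, which gives 30 patients and 120 sweeps. Nothing in this depends on which arteries are imaged.

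**2. Slack.** At 4 sweeps per patient: 120 − 118 = 2 (2/120 = 1.7%). At 5 per patient: 150 − 118 = 32 (32/150 = 21.3%). Four is a minimum.

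**3. Precision if some sweeps are set aside, at 120 sweeps.** The two whole counts either side of 0.93n are shown.

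| Assumed u | Target sweeps | 0.93n | Exact 95% widths |
|---|---|---|---|
| 0 | 120 | 111.60 | 0.1027 (111), 0.0979 (112) |
| 10% | 108 | 100.44 | 0.1082 (100), 0.1025 (101) |
| 20% | 96 | 89.28 | 0.1147 (89), 0.1078 (90) |
| 50% | 60 | 55.80 | 0.1562 (55), 0.1435 (56) |

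With all 120 sweeps, one success fewer already moves the width from 0.0979 to 0.1027, about the lower end of the 10% row.

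**4. Shift if everything is pooled.** Shift = u × (s − 0.93). With s = 0.88 or 0.98:
- u = 0.10: 0.10 × (∓0.05) = ∓0.005.
- u = 0.20: 0.20 × (∓0.05) = ∓0.010.
- u = 0.50: 0.50 × (∓0.05) = ∓0.025.

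For scale, the simple binomial standard error at 120 sweeps is √(0.93 × 0.07 / 120) = 0.023. The first two shifts are less than half of that.

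**5. Does an unreachable artery cost a sweep?** The Methodology list holds the aorta, two iliac arteries, and the internal and external iliac arteries. That is seven vessels if the last pair is counted on both sides (1 + 2 + 4), and five if it is not (1 + 2 + 2). Either number exceeds the minimum of four sweeps, so at that minimum a full list requires at least one sweep to show more than one artery. Losing an artery therefore need not remove a sweep, and u may be well below the share of arteries that cannot be reached.

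**The case for a change.** The strongest argument for changing the plan is that this proportion is its only quantitative test of the algorithm, and that the robotic cohort follows a successful evaluation of the first 30 patients. If the countable sweeps are chosen after the Dice values are known, two analysts could report different rates from the same recordings. A few sentences written beforehand would prevent that at almost no cost.

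Part of this stands. The two sections are in tension, main pelvic arteries is undefined in the summary, and the fallback to other arteries is not expressly confined to the robotic cohort.

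The rest is weaker. The plan does name a denominator, every sweep pooled, and a success rule applied to each sweep, so the default analysis is determined. The comparability assumption rests on a scanning protocol that a summary would not be expected to reproduce, and that protocol may already list the segments. The fallback sentence may be meant mainly for the robotic patients, who are outside the calculation of 118. The stated aim is also vessel segmentation in general, so a pooled rate is not foreign to it.

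The obvious remedy has difficulties of its own. Assigning each sweep to a single artery presumes a one-to-one match that the documents do not state. Dividing by every acquired sweep of named arteries would also fix a denominator with no limit to sweeps kept out of training, although the Methodology section puts all recorded data to training use.

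**Conclusion.** No change to the plan follows. This is a gap in a summary that analysts can fill sensibly: apply the stated rule to all sweeps, say which arteries they show, and give the interval width achieved. The 118 sweeps and 30 patients are correct and unaffected.

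With 10% to 20% of sweeps showing other arteries, the width rises from the planned 0.10 to at most about 0.115, or the pooled rate moves by 0.5 to 1 point either way. A share near one half would matter more (width about 0.144 to 0.156, shift 2.5 points), but nothing in the documents suggests it: the pelvic vessels are the named targets and other arteries the alternative.

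The conclusion rests on assumed shares, an assumed 5-point difference in success, the minimum of four sweeps per patient, and a simple binomial interval that treats sweeps as independent. Following the plan as written is not shown to give a wrong result.
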